4.3 Study Enrollment Procedures at University of Connecticut Health Center

Study recruitment and enrollment. The study is a single-site randomized clinical trial that will be performed at the University of Connecticut Clinical Research Unit. Patients will be recruited from a variety of sources as described below. Three hundred patients will be enrolled into the trial in order to randomize 200 patients and complete 140 patients at 3 years of randomized treatment. Based on our prior experience in studying patients in this age group with hypertension and mild mobility issues, we project a 3-year attrition rate of approximately 30%. Recruitment will be carried out by several mechanisms, including: A) contacting former research participants from the Cardiology and Hypertension faculty practices, the Center on Aging, and Neurology who have agreed to be informed of future studies, B) publically posted advertisements in addition to advertisements on the internet, radio and newspapers, C) Recruitment presentations conducted at community health centers, faith-based organizations and senior centers in conjunction with BP community clinics.

Recruitment will be extended into the greater Hartford region to improve minority participation. Advertisements will state that we are seeking volunteers for a treatment study aimed at older patients with hypertension willing to join a study involving the evaluation and treatment of high blood pressure, mobility and cognitive function. The

ads will state that antihypertensive medication, clinical visits, brain imaging, and other testing will be provided at no cost.

Following voluntary assent, interested individuals will be screened by phone for inclusion/exclusion criteria. Those meeting initial screening criteria will be invited to a Consent/Evaluation Visit during which informed consent will be obtained, followed by a medical history, physical exam, and tests to determine eligibility. Those not meeting study criteria will be referred for medical care. Patients not able to read and understand the consent form will be excluded from the study.

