5.6.4 Completion/Final Evaluation

Visit 9 (36 months post-randomization) - Patients will return for evaluation of antihypertensive response to therapy according to randomized treatment group and will have final research testing for WMH, mobility, cognitive function as well as blood pressure control. Procedures previously defined above will be done at this visit:

- Medical history, concomitant medications, adverse events, medication compliance
- Standardized clinic BP measurements, body weight and height
- Antihypertensive medication will be prescribed/continued according to clinical goals for long-term management. Clinical follow-up will be arranged with either primary care physician, one of the study physicians, or both, depending on wishes of study patient.
- Safety laboratory studies (potassium, creatinine, BUN) if clinically necessary
- Electrocardiogram
- Ambulatory blood pressure monitoring
- MRI acquired at UCONN neuroradiology
- Mobility Testing
- Cognitive Testing
- Questionnaires related to urinary function, QOL

- Home BP monitoring

Early termination patients who complete at least 18 months of randomized therapy will be considered completed study patients and all comprehensive tests will be completed that were designated for visit 9.

SAFETY ASSESSMENTS

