6. INTERVENTION DISCONTINUATION

- A. Patients will be discontinued from their antihypertensive intervention if it is deemed that the treatment(s) or blood pressure level is no longer safe or appropriate based on clinical condition (e.g. development of congestive heart failure that mandates a specific regimen or development of a terminal malignancy).
- B. Potential reasons for discontinuation of the intensive treatment might include untoward symptoms associated with low blood pressure related to development of a new morbidity (e.g. blood loss, sepsis) or intolerance to therapy (e.g. lightheadedness/syncope. In rare cases, hyperkalemia or hyponatremia may develop that would be unmanageable under the constraints of the protocol-drive therapies. Hypokalemia will be managed with aggressive potassium replacement to maintain serum levels > 3.5 meq/L.
- C. As this is an intention-to-treat trial, patients who discontinue treatment interventions will be invited to participate in clinical follow-up and all comprehensive outcome studies at months 18 and 36 of the trial.
- D. In the event of temporary discontinuation of antihypertensive treatment (e.g. need to withhold antihypertensive medications due to surgery, post-operative bleeding, infection or other causes of low blood pressure), reassessment of these individual patients will be made

in the research clinic for a return of BP levels towards baseline, and study medications will then be resumed.

[figure not shown]

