7. STATISTICAL CONSIDERATIONS

7.1 General Design Issues

General considerations: Predictor, covariate, and dependent variables will be examined for outliers and data beyond the range of human performance. We will analyze variables on the original measurement scale, or on a scale that allows meaningful interpretation e.g., when an inverse transformation on a time measure results in a speed interpretation. The primary analyses (hypotheses 1, 2 and 3) will be intention-to-treat.

Hypothesis models, analysis plan, and power estimates for primary outcomes were developed with PASS 2008³⁵ and SAS PROC POWER³⁶ were used for estimation of power.

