8.2 Hypotheses and Statistical Analyses

The Figure shows graphically how our hypotheses relate to one another. Hypothesis 1 tests the combined effects of paths A, B, C, D & E i.e., the total effect of BP on mobility. Hypothesis 2 tests path A, Hypothesis 3 tests path D, Hypothesis 4 tests path B+E; together Hypotheses 2, 3 and 4 together test the effect of BP on mobility mediated through BP's effects on WMH and WM microstructure. Hypothesis 5 tests the relative importance of paths A and B to that of path C, i.e., the degree to which the effect of BP on mobility is explained by WMH. Hypothesis 6 tests the relative importance of paths D and E to that of path C, i.e., the degree to which the effect of BP on mobility is explained by changes in WM microstructure.

Hypothesis path diagram

Hypothesis 1: Intensively treating 24-h systolic BP to a goal of <130 mmHg versus standard BP control of <145 mmHg will lead to faster walking speeds at T₃₆. (Paths A&B+C+D&E)

Hypothesis 2: Intensively treating 24-h systolic BP to a goal of <130 mmHg versus standard BP

control <145 mmHg will lead to smaller total WMH volume. (Path A)

Hypothesis 3: Intensively treating 24-h systolic BP to a goal of <130 mmHg versus standard BP

control <145 mmHg will stabilize brain WM microstructural integrity (FA and MD) at T₃₆. (Path

D) We will perform 3 sets of analyses for hypotheses 1, 2 & 3:

- a. Multiple linear regression will be performed with treatment group (intensive vs. standard) as the predictor of interest. Gait velocity at T₃₆ is the primary outcome for hypothesis 1, WMH at T₃₆ is the primary outcome for hypothesis 2, and DTI indices (FA and MD) are the primary outcomes for hypothesis 3. The analysis will be intention-to-treat. Age, sex, and 24 hour SBP at T₀ (baseline) will be included as covariates, along with other demographic factors for which the treatment groups are not comparable. **The analysis for hypothesis 1 is the proposal's primary efficacy analysis and thus the proposal is powered to address this analysis (see Sample size estimation).**

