Product of coefficients methods^{35,36} will be used for formal statistical inference regarding the mediation. Specifically, we will estimate the product of the effect estimated for hypothesis 2 corresponding to Path A (the effect of intervention group on total WMH at T₃₆), and the effect estimated for hypothesis 3 corresponding to Path B (the effect of WMH at T₃₆ on gait velocity at T₃₆). The magnitude of this product turns out to be proportional to the change in the effect of intervention group on gait velocity at T₃₆ when WMH at T₃₆ is added to a regression model of gait velocity at T₃₆ as a function of intervention group. Similar models will be used to assess outcomes at T₁₈, and the cognitive outcomes. As formal tests for mediation using the product of coefficients method require larger sample sizes than available in this study, we will treat results from analyses in Hypothesis 5 as preliminary, to be potentially verified by a larger study should the main effects in Hypotheses 1-3 be confirmed.

Hypothesis 6: Diffusion tensor imaging (DTI) indices (FA, MD) at T₀ and at T₃₆ mediate the effect of treatment group, showing that the mechanism by which reduced ABP is linked to better mobility occurs by preserving brain WM microstructural integrity (FA, MD).

(Paths C – D&E) The same analysis as used for hypothesis 5, except that the mediating effect of the DTI indices will be assessed.

Missing Data.

Death and study attrition are associated with age-related diseases. Failure to account for this informative censoring may result in biased estimates of dementia risk and cognitive decline.³⁷ Hence, we will collect data by telephone to assess the degree to which living participants who fail to appear for their final assessment differ from participants who complete the study. As mentioned above, we will use telephone administration of a validated mobility assessment³⁹ and the method developed by [name] and colleague³⁰ to estimate mobility outcomes through multiple imputation or joint modeling that would have been

observed had the participants appeared for their clinical assessment. While our primary efficacy outcome analysis will be limited to participants who complete the study, this will be the first trial in aging with the potential to assess the impact of informative dropout beyond usual sensitivity analyses.

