8.3 Sample Size and Randomization

We conservatively estimate that at least 140 of the original 200 participants will complete assessments at 35 months. We analyzed a subset of participants in our earlier observational study in order to mimic the results of the two treatment groups we expect to see in the intervention study. For a standard care arm, we selected participants in the observational study who had 24 hour systolic BP between 140 and 150 mmHg, inclusive, at follow-up, and for the intensive treatment arm, we selected participants with 24 hour Systolic BP between 120 and 130 mmHg, inclusive, at follow-up. A regression of gait velocity over 8 feet on our covariates age, sex, and 24 hour systolic BP at baseline showed an r^2 of 0.1267. If we see similar results in the intervention study, 140 participants (70 in each group) will give us 85% power to observe an increase in r^2 of 0.0533 to 0.1800. In our prior observational study, we saw an increase in r^2 of 0.1082 to 0.2349, with a difference in gait speed between the two simulated treatment groups of 0.15m./sec. While the 0.15m/sec gait speed difference between the low and high BP groups appears small, it represents only 2 years of observation. Mobility impairment linked to WMH is a long-term decremental process that limits gait velocity over 10 or more years. Thus a “small” 2-year differential is both believable and meaningful. We are therefore confident that the proposed study has ample power to find smaller yet clinically significant effects for our primary outcome. A regression of total WMH on covariates age, sex, and 24 hour systolic BP at baseline showed an r^2 of 0.1162. Similar results in the intervention study imply 85% power to observe an increase in r^2 of 0.0540 for the effect of the treatment arm, to 0.1702. We actually observed an increase of 0.0861, to 0.2023, in the prior observational study, corresponding to a difference between the two simulated treatment groups of 0.93% total WMH.

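### The primary month-36 gait regression is labelled intention-to-treat but restricted to completers; 5.6.4 and 8.2b disagree on who completes, and baseline gait is not a listed covariate

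*Protocol*

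**What the plan says.** **Label.** Protocol 7.1 states: "The primary analyses (hypotheses 1, 2 and 3) will be intention-to-treat". Section 8.2, analysis a, repeats the label for the regression of gait velocity at month 36 and calls it the "primary efficacy analysis and thus the proposal is powered to address this analysis".

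**Restriction.** The Missing Data paragraph of 8.2 warns that ignoring informative censoring can bias estimates. It plans telephone follow-up of living patients who miss the final assessment, with multiple imputation or joint modelling. It then sets the primary analysis apart from that work: "While our primary efficacy outcome analysis will be limited to participants who complete the study".

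**Who completes.** Section 5.6.4 gives a rule: "Early termination patients who complete at least 18 months of randomized therapy will be considered completed study patients". Those patients receive the visit 9 tests when they leave. Section 8.2b says that for patients present at month 18 but not month 36, the month-18 data serve to estimate the effect of informative loss. Section 6, item C, opens by calling the trial intention-to-treat and adds that "patients who discontinue treatment interventions will be invited to participate in clinical follow-up and all comprehensive outcome studies at months 18 and 36". The two projections are "randomize 200 patients and complete 140 patients at 3 years of randomized treatment" (4.3) and "at least 140 of the original 200 participants will complete assessments at 35 months" (8.3).

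**Covariates.** Analysis a lists age, sex and baseline 24-hour systolic BP, which "will be included as covariates, along with other demographic factors for which the treatment groups are not comparable". Gait is not a demographic factor. The mobility battery at baseline visit 2 (5.6.2) includes gait speed, and the précis and section 3 state the mobility outcome as change from baseline.

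**The concern.** The primary estimate leaves out roughly 30% of those randomised, in a trial whose own text expects the missing patients to differ. The month-18 analysis (8.2b), the three-visit mixed model (8.2c) and the telephone-based methods address this, but none of them enters the primary estimate.

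The boundary of the set is also open at one point. A patient who leaves at month 20 and has the visit 9 tests on exit is completed under 5.6.4 and lost under 8.2b. No passage says whether that exit gait counts as a month-36 value, so two statisticians could analyse different patients and different measurements for the primary endpoint.

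Leaving out baseline gait gives up precision at no saving. Among completers it also gives up an adjustment for selection related to starting gait.

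**Working it through.** **1. Reproduce the stated power.** Inputs from 8.3: covariate R² 0.1267, increase 0.0533 to 0.1800, n = 140. A two-sided alpha of 0.05 is assumed, since none is stated.
- f² = 0.0533 / (1 − 0.1800) = 0.0650
- noncentrality = 140 × 0.0650 = 9.10, with df 1 and 135
- power = 0.850

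The stated 85% is right, and it is power for 140 completers: 200 × (1 − 0.30) = 140.

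**2. Scale in m/s.** The prior cohort showed 0.15 m/s for an R² increase of 0.1082 (8.3). With equal groups and group uncorrelated with the covariates:
- SD = 0.15 / (2√0.1082) = 0.228 m/s
- detectable difference = 2 × 0.228 × √0.0533 = 0.105 m/s

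This SD is a ceiling. If the covariates explain 30% of group membership in that cohort, SD is 0.191 and the detectable difference 0.088. The m/s figures below then shrink in proportion, and the percentages do not change.

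**3. Add baseline gait.** No document gives the correlation ρ between baseline and month-36 gait. If both relate to the covariates alike, the partial correlation is r = (ρ − 0.1267) / (1 − 0.1267). Then f² = 0.0533 / [0.82 × (1 − r²)], with df 1 and 134.

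| ρ (assumed) | r | f² | power |
|---|---|---|---|
| 0.3 | 0.198 | 0.0677 | 0.863 |
| 0.5 | 0.427 | 0.0795 | 0.912 |
| 0.6 | 0.542 | 0.0920 | 0.946 |
| 0.7 | 0.657 | 0.1142 | 0.978 |

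**4. Bias from using completers only.** Let p be the share lost in an arm and g the amount by which its completers outpace those lost. The completer mean exceeds the all-randomised mean by p × g, so the bias in the difference is p₁g₁ − p₂g₂.
- 30% lost in each arm, same gap: 0
- 35% vs 25%, gap 0.10 m/s in both: 0.035 − 0.025 = +0.010 m/s; arms reversed, −0.010
- 30% in each arm, gaps differing by 0.05 m/s: 0.30 × 0.05 = 0.015 m/s, sign set by the arm with the larger gap

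**5. Simulation of the 8.2a regression.** No treatment effect, 100 per arm, 30% loss overall, of which 10 percentage points are random before month 18 and the rest is driven by month-18 gait. Visit correlations are 0.6, 0.7, or 0.7 falling to 0.5.
- Same mechanism in both arms: about 0.001 m/s or less.
- Moderately different strength (log-odds per SD 1 vs 0.5, 1.5 vs 1, 2 vs 1), or 35% vs 25% loss: 0.006 to 0.015 m/s. That is 6-14% of 0.105 and under half the standard error of 0.036. False-positive rates are 5.4-7.6%.
- Arms reversed: similar size, negative sign.
- Correlation 0.3: 0.001 to 0.004 m/s.

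Adding baseline gait removes about 36-65% of the bias at the higher correlations. The three-visit model with unstructured covariance leaves at most 0.0014 m/s when loss depends on month-18 gait. If loss depends on unseen month-36 gait and differs in strength between arms, it keeps 0.009-0.013 m/s, against 0.016-0.019 for 8.2a.

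**6. Covariance in 8.2c.** Under purely random loss, with correlation falling from 0.7 to 0.5, a random intercept alone gave an 8.7% false-positive rate, against 4.5% with unstructured covariance.

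**The case against.** Several stronger readings are tempting, and the documents do not support them.

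- **Three competing definitions of completion.** A reader might set 4.3, 5.6.4 and 8.3 against each other. But 4.3 and 8.3 are planning projections, not inclusion rules. The Missing Data text contrasts completers with living patients who miss the final assessment, which fits 6.C, 8.3 and a month-36 outcome. What stands is 5.6.4 against that reading and against 8.2b.
- **An empty intention-to-treat label.** Item 6.C ties the term to inviting patients who stop treatment to the month 18 and 36 tests. That supports analysing those assessed as randomised, although it is not a formal analysis-set definition.
- **An analysed set anywhere from 140 to 180.** The upper figure needs an assumed 20 losses before month 18 and exit tests counted as month-36 values, a reading that 8.2b disfavours.
- **SAP item 2a displaces the protocol regression.** Its primary label most naturally marks the main analysis within that item. The SAP says it adds secondary analyses, and it never withdraws 8.2a.
- **A bias that favours intensive treatment.** No document gives loss by arm, so neither size nor sign is known.

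It is also fair that omitting baseline gait is valid under randomisation, and that 8.2c allows further random effects if they improve fit. An all-randomised likelihood model has its own cost: it implicitly projects month-36 gait for patients who died. The label, the 5.6.4 conflict and the free gain in precision survive all of this.

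**Conclusion.** The point holds as a should-fix. The intention-to-treat label and the completer restriction need one explicit reconciliation, 5.6.4 conflicts with 8.2b over early leavers, and baseline gait is missing from the primary model. These three findings rest on the text alone.

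The power gain, from 85% to about 86-98%, rests on assumed correlations of 0.3-0.7. The bias is conditional: near zero with like mechanisms, roughly 0.006-0.015 m/s in either direction for moderate differences between arms at correlations of 0.6-0.7, and smaller at lower correlation. Only loss driven by gait in one arm alone gave larger values (0.021-0.038 m/s), and nothing in the documents points to that case. The sample-size arithmetic is not at fault.

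**What to change.** 1. Add baseline gait as a covariate in 8.2a.
2. State that everyone with a month-36 gait assessment is analysed as randomised, whatever their treatment status. Reconcile 5.6.4 with the Missing Data text and 8.2b, and record early-exit tests at their actual month, not as month-36 values.
3. Report the three-visit model of 8.2c on all randomised participants, with unstructured covariance, as the main check on the completer regression, or in its place if the sponsor prefers. State that it assumes missing at random, and state how deaths are handled, because it otherwise projects gait after death.
4. Keep the planned telephone-based imputation or joint model as the missing-not-at-random sensitivity analysis.
5. A minor addition: one sentence confirming that 8.2a remains the primary gait test alongside SAP item 2a.

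The cost is protocol and SAP wording, settled before the October 2018 database lock that the SAP names. Gait at baseline, month 18 and month 36 is already scheduled and 8.2c is already written, so no new data are needed. Replacing the primary model, as opposed to adding the check, would be a larger change that close to lock.

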8.3 Sample Size and Randomization

We conservatively estimate that at least 140 of the original 200 participants will complete assessments at 35 months. We analyzed a subset of participants in our earlier observational study in order to mimic the results of the two treatment groups we expect to see in the intervention study. For a standard care arm, we selected participants in the observational study who had 24 hour systolic BP between 140 and 150 mmHg, inclusive, at follow-up, and for the intensive treatment arm, we selected participants with 24 hour Systolic BP between 120 and 130 mmHg, inclusive, at follow-up. A regression of gait velocity over 8 feet on our covariates age, sex, and 24 hour systolic BP at baseline showed an r^2 of 0.1267. If we see similar results in the intervention study, 140 participants (70 in each group) will give us 85% power to observe an increase in r^2 of 0.0533 to 0.1800. In our prior observational study, we saw an increase in r^2 of 0.1082 to 0.2349, with a difference in gait speed between the two simulated treatment groups of 0.15m./sec. While the 0.15m/sec gait speed difference between the low and high BP groups appears small, it represents only 2 years of observation. Mobility impairment linked to WMH is a long-term decremental process that limits gait velocity over 10 or more years. Thus a “small” 2-year differential is both believable and meaningful. We are therefore confident that the proposed study has ample power to find smaller yet clinically significant effects for our primary outcome. A regression of total WMH on covariates age, sex, and 24 hour systolic BP at baseline showed an r^2 of 0.1162. Similar results in the intervention study imply 85% power to observe an increase in r^2 of 0.0540 for the effect of the treatment arm, to 0.1702. We actually observed an increase of 0.0861, to 0.2023, in the prior observational study, corresponding to a difference between the two simulated treatment groups of 0.93% total WMH.

8.3.1 Treatment Assignment Procedures

This trial is an open-label PROBE design – clinical staff and investigators will be aware of treatment assignment for safety and management. Those observers performing outcome tests (WMH calculations, mobility testing, cognitive assessment, and urinary function testing) will remain blinded to individual treatment group assignments until the end of the trial. .Interim analyses and Stopping Rules

8.3.2 Interim Analyses and Stopping Rules For Safety

No interim analysis is planned that would result in stopping the trial early.

Stopping rule for safety. A decision to discontinue the study will be based primarily on serious adverse events (SAEs). In discussion with the DSMB as it relates to timing of any decision making, the study will be stopped if unexpected and possibly study-related SAEs occur in 20% or more of the study population, or if an imbalance of these SAEs occur in 15% or greater of those participating in either treatment arm. We anticipate that unexpected and possibly study-related SAEs will be rare, because participants will be receiving well tolerated antihypertensive therapies with substantial clinical safety oversight by the PI and research staff. Research nurses and staff who assist in the conduct of the trial will detect SAEs. In addition to the immediate disclosure, complete reports of SAEs will be reviewed at monthly staff meetings with the PIs, research nurses and physicians.

